11.2 Design Considerations and Data

This is a subject-level historically controlled, prospective, non-randomized Phase I/II clinical trial to assess the safety and efficacy of autologous transplantation of CD34+ cells originated from the bone marrow of ADA-SCID infants and children following human ADA cDNA transfer by the EFS-ADA lentiviral vector.

Descriptive results will be presented for the study cohort.

Comparisons will be made to three cohorts:

- 1) A historical control group consisting of ADA-SCID HSCT-treated subjects lacking a medically eligible HLA-matched sibling/family donor and treated at GOSH/UCL (UK) or Duke University Children's Hospital, North Carolina Transplant Center (USA) from the year 2000 onward
- 2) A historical control group consisting of ADA-SCID HSCT-treated subjects having a medically eligible HLA-matched sibling/family donor and treated at GOSH/UCL (UK) or Duke University Children's Hospital, North Carolina Transplant Center (USA) from the year 2000 onward
- 3) All HSCT-treated subjects from GOSH/UCL or Duke University Children's Hospital, who were treated with HSCT from the year 2000 onward, with any type of donor

Details on the historical HSCT control groups from GOSH/UCL and Duke University Children's Hospital can be found in [Appendix H](#).

Statistical analyses will be performed, and their outcomes presented, in three stages:

- Interim look – 6 months
 - Descriptive statistics for all available subjects
- Primary analysis - Comparison on primary efficacy endpoints to the HSCT control cohorts—12 month follow-up analysis
 - Descriptive statistics for the complete study cohort, with all patients having reached at least 12 month follow-up
 - Comparison to HSCT control cohorts on safety, primary efficacy endpoints and need of immunoglobulin replacement (IgRT) (main secondary efficacy endpoint).
- End of study analysis:
 - Descriptive statistics for the complete study cohort, with all patients having completed the study (24-month follow-up)
 - Comparison to HSCT control cohorts on safety, primary efficacy endpoints and need of immunoglobulin Replacement (IgRT) (main secondary efficacy endpoint).

In each study stage and for all analyses, all relevant data available will be used.

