11.5 Analysis Sets

11.5.1 Safety Analysis Set

The safety analysis set will consist of all patients treated with OTL-101 at UCLA/NIH (current study cohort) and the complete HSCT historical control cohort, consisting of ADA-SCID subjects with any type of donor treated with HSCT at either GOSH/UCL (UK) or Duke University Children's Hospital (USA) from the year 2000 onward.

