11.6.2.3 Safety Analyses

Safety will be analyzed descriptively by arm over time for the safety population. Coding will be done using current MedDRA version or higher. AEs, including SAE's will be presented by:

- System organ class and preferred term

Where appropriate, shift tables will be presented for laboratory parameters, vital signs and physical examination.

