This information is only available from the patient's records; we therefore plan to re-consent these patients to access their full medical records, and share the information with regulatory agencies and pharmaceutical companies.

4. Data to be collected – Duke University Children's Hospital

Duke University maintain a database of information on patients who have received HSCTs. 10 treated patients have been identified between 2000-2016. The patients have previously given consent to their data being entered into this database and being used for other ethically approved studies.

The following data will be collected from this control group:

- Demographics (gender, year of birth, age at presentation to site),
- Diagnosis (age at and method of ADA-SCID diagnosis),
- HSCT history, including: age at transplant, type of transplant cells and number, donor type and outcome, need for a second transplant, outcome of vaccinations post-transplant,
- Use of PEG-ADA ERT and immunoglobulin therapy (before and after transplant), including time since transplant if reinitiated post HSCT,
- Graft versus host disease,
- Listing of relevant medical history, including infections (severe, recurrent or opportunistic infections) and neurological conditions,
- Previous and Concomitant Treatment,
- Changes in Medical Condition post HSCT, including severe/opportunistic infections, emergent neurological events, autoimmune conditions, oncologic disease, SAEs, bone/skeletal deformities, physical developmental delays or weight loss,
- Lymphocyte subsets (CD3, CD4, CD8, CD19, CD56/CD16 and CD4+/CD45RA cell counts) at baseline and at 1-8 months, 9-16 months and 17-30 months post HSCT,
- ADA activity & ADA metabolites (plasma deoxyadenosine, ADA activity in RBCs, dAXP) at baseline and at 1-8 months, 9-16 months and 17-30 months post HSCT,
- Death and reason for death.

5. Data collection process

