7.2 Safety Population

The safety population will consist of all subjects treated with OTL-101 at UCLA/NIH (current study cohort) and the complete HSCT historical control cohort consisting of ADA-SCID patients with any type of donor treated with HSCT at either GOSH or Duke University from the year 2000 onwards.

8 Statistical Methods

In general, continuous variables will be summarised using the mean, standard deviation, median, minimum, maximum and number of subjects. Categorical variables will be summarised using number of subjects and percentages.

For all summaries, the HSCT controls will be summarised in the groups of those without a matched related donor, those with a matched related donor and all subjects.

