8.4.1.3 Adverse Events

Treatment emergent adverse events will be summarised in an overall summary presenting the number (%) of subjects with:

- any AE,
- AE grade 2 or higher (at least moderate in severity),
- AE grade 3 or higher (at least severe in severity),
- treatment related AE,
- AE leading to study withdrawal,
- any serious adverse event (SAE),
- treatment related SAE,
- SAE leading to death.

Incidence and frequency of treatment emergent AEs will be summarised by system organ class (SOC) and preferred term (PT):

- overall,
- by maximum severity,
- by maximum relationship to treatment,
- treatment related AEs,

Final Version 4.0 Page 23 of 27

AEs leading to study withdrawal (if sufficient events).

In addition, a summary table for the most frequently reported treatment emergent adverse events (those reported in 2 or more subjects) will be presented by PT in descending order of incidence and frequency.

In each table, if the same SOC or PT is reported on multiple occasions for a single subject, it will only be included once in the summary. In the table by maximum severity, only the most severe occurrence for each SOC and PT for each subject will be included in the summary. In the table by maximum relationship, only the most related occurrence for each SOC and PT for each subject will be included in the summary.

Any adverse events that are not treatment emergent (occurred prior to the infusion) will be listed.

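### Non-serious AE rates for the pooled HSCT controls would be understated, because Appendix H lists general AE collection at GOSH but not at Duke and the plan does not separate the two

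*Protocol*

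**What the plan says.** **Collection.** Protocol Appendix H gives a separate data list for each control site. For GOSH (25 patients) the items to come from medical records include AEs and SAEs, autoimmune disease, oncologic disease or leukaemia, infections, and death with its reason. Access to those records needs re-consent. For Duke (10 patients) the safety items are graft versus host disease, infections, death with its reason, and "Changes in Medical Condition post HSCT, including severe/opportunistic infections, emergent neurological events, autoimmune conditions, oncologic disease, SAEs". That last item continues with skeletal deformities, developmental delay and weight loss. The Duke list has no general AE entry. Neither list mentions AE grade or relationship to treatment.

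**Populations.** Protocol 11.5.1: "The safety analysis set will consist of all patients treated with OTL-101 at UCLA/NIH (current study cohort) and the complete HSCT historical control cohort". SAP 7.2 likewise includes "the complete HSCT historical control cohort consisting of ADA-SCID patients with any type of donor treated with HSCT at either GOSH or Duke University". Neither makes membership depend on whether AE data exist.

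**Analysis.** Protocol 11.6.2.3: "Safety will be analyzed descriptively by arm over time for the safety population", with AEs by SOC and PT; Protocol 11.6.3 repeats this at the primary analysis. Protocol 11.2 plans a "Comparison to HSCT control cohorts on safety, primary efficacy endpoints and need of immunoglobulin replacement (IgRT"). The opening of SAP section 8 states: "For all summaries, the HSCT controls will be summarised in the groups of those without a matched related donor", then those with such a donor, then all subjects. There is no split by site. SAP 8.4.1.3 sets out rows such as any AE, "AE grade 2 or higher (at least moderate in severity"), grade 3 or higher and treatment-related, followed by SOC/PT tables.

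**The concern.** A patient whose non-serious events were not collected cannot appear in a numerator. If that patient still counts in the denominator, lack of collection reads as absence of the event. OTL-101 subjects have AEs sought prospectively at every scheduled visit (Protocol 9.4.1). A side-by-side table of non-serious, graded or related AEs would then partly show how the data were gathered at each centre, and the control column would look cleaner than it should.

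Duke was added as a control site in SAP version 4.0. The changes listed for that version (SAP 10.2) adapt the time-to-event calculations for missing dates. For AEs they change only the MedDRA version.

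**Working it through.** The documents give no AE rate, safety margin or safety power, so there is no planned figure to reproduce. The check is a dilution calculation followed by a reading of whether controls belong in the tables.

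**Inputs.** GOSH 25 and Duke 10 (Appendix H), 35 in total; Duke share 10/35 = 28.6%. Assumed: *p*, the true proportion with a given non-serious event, equal at both sites; *f*, the share of Duke events captured relative to GOSH, from 0 to 1; and AE records available for all 25 GOSH patients.

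**Formula.** Displayed control proportion = *p* × (25 + 10*f*)/35.

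| *f* | 0 | 0.25 | 0.5 | 0.75 | 1 |
|---|---|---|---|---|---|
| Factor | 0.714 | 0.786 | 0.857 | 0.929 | 1.000 |
| *p* = 30% shows as | 21.4% | 23.6% | 25.7% | 27.9% | 30% |
| *p* = 50% shows as | 35.7% | 39.3% | 42.9% | 46.4% | 50% |
| *p* = 80% shows as | 57.1% | 62.9% | 68.6% | 74.3% | 80% |

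With equal true rates in both arms and *f* = 0, OTL-101 would look worse by 8.6, 14.3 and 22.9 percentage points for the three values of *p*.

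**Any-AE row.** A Duke patient enters this row through an SAE or a named condition. If every control truly had some AE, and 50% to 95% of Duke patients had a captured event (assumed), the row shows (25 + 5)/35 = 85.7% to (25 + 9.5)/35 = 98.6%. The loss here is smaller than for an individual non-serious PT.

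**SAEs and deaths.** Both are listed for both sites, so *f* = 1 by design and the factor is 1.

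**Donor groups.** At *f* = 0 the factor within a group is 1 minus Duke's share of that group. The site mix by donor type is not given, so dilution against the controls without a matched related donor is unknown.

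**Re-consent at GOSH.** If AE records were obtained for only 20 or 15 GOSH patients (assumed) and all 35 stayed in the denominator, the factor at *f* = 0 would be 20/35 = 0.571 or 15/35 = 0.429.

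**Are controls in the AE tables?**
- For: the pooled safety population, the rule covering all summaries, and Protocol 11.2, 11.6.2.3 and 11.6.3. The SAP usually says so when it means OTL-101 alone (for example RCL, haematology, biochemistry, vital signs); its AE sections carry no such limit.
- Against: SAP 8.4.1.1 summarises AEs by treatment emergence, counted only from the OTL-101 infusion, which no control received. SAP section 6 lists survival, event-free survival, IgRT and infection rate as the control comparisons at the primary and end-of-study analyses, without safety. The data-analysis part of Appendix H likewise has no general AE comparison.

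The documents do not settle it.

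**The case against.** The strongest reply is that the AE tables may be for OTL-101 only. No AE table text states a control denominator. The SAP names the control groups where it wants them shown, as in demography, survival, IgRT and infections, and does not name them under AEs. The emergence rule cannot be applied to controls, and a row for study withdrawal fits retrospective patients poorly. This stands as far as it goes: the denominator of 35 is an inference. It does not remove the point, because the protocol plans AE summaries by arm and a safety comparison, and the SAP neither carries that out nor drops it.

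Second, zero capture at Duke is a worst case. The Duke item is worded as an open list, graft versus host disease is separate, and Appendix H says both sites draw on databases and patient records. This stands, and it is why the size is a range. Where control data may be thin, the SAP says so for IgRT and infections; it has no such wording for AEs.

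A reader might infer that the safety comparison as a whole is distorted, or that only SAEs are common to both sites. The documents support neither. The primary safety parameter is SAEs, listed at both sites, as are deaths, severe or opportunistic infections, autoimmune disease and oncologic disease. The safety analysis is descriptive, with no test or decision rule, and the artefact works against OTL-101, so it cannot produce a falsely favourable safety claim from this source.

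**Conclusion.** The point holds for the all-AE, graded, related and SOC/PT tables, if these include all controls. In the all-controls column, rates of non-serious events outside the Duke categories are then understated by a factor between 0.71 and 1. This assumes equal true rates at the two sites and complete GOSH records. Where in the range it falls depends on Duke capture, which the documents do not state, and the donor-group columns cannot be sized.

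SAEs and deaths are untouched by the difference between the lists. They would still be understated if GOSH patients without re-consented records were counted as event-free.

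Separately, the SAP needs clarifying whichever reading is right. It gives controls no emergence date, and it omits a safety comparison that the protocol promises. This is worth correcting before the tables are programmed, but it does not undermine the primary safety evaluation of OTL-101.

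**What to change.** In SAP 8.4.1 and the table shells:

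1. Limit the side-by-side comparison with HSCT controls to deaths, SAEs and the conditions collected at both sites: severe or opportunistic infections, autoimmune disease and oncologic disease. Split control SAEs by severity or relationship only if those items are in fact collected.
2. Show the all-AE, graded-AE and related-AE tables for OTL-101 alone. If GOSH AEs are reported, put them in a separate, labelled column.
3. For each data type, use as denominator only the controls whose records were available for it, and report that number. This applies to GOSH as well as Duke, because GOSH AE data need re-consent.
4. Define emergence for controls from the date of transplant, or age at transplant where dates were not recorded.
5. Reconcile SAP section 6 with Protocol 11.2 on whether safety is compared with controls.

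If a GOSH AE column is shown with complete records, its denominator is 25 instead of 35 and the dilution factor returns to 1. The cost is SAP wording and table shells. The non-serious AE comparison with Duke is given up, but the Duke collection list has no general AE item to support it.

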17.9 Appendix I: List of Protocol Changes

Changes made 23 April 2013 (ver. 1.3) from previous version dated 8 October 2012 (ver. 1.2)

1. Remove measurement of plasma ADA levels as follow-up test
Reason: subjects are withdrawn from PEG-ADA ERT 30 days post infusion of gene-modified cells, and thus, this test would not be informative
Protocol pages affected: 51, 66, 71, 72, 110, 111, 117
2. Remove ophthalmologic exam from baseline screen
Reason: not needed
Protocol pages affected: 70, 110, 111
3. Remove CBC test from Day 0 (Day of Infusion)
Reason: not needed, subjects already have a CBC drawn on Day +1
Protocol pages affected: 72
4. Subjects who discontinue study will be replaced (previously were not replaced)
Reason: would allow treatment of 10 subjects
Protocol pages affected: 80
5. Add identity test to characterization of final product
Reason: per FDA request
Protocol pages affected: 57
6. Change criteria for reinstating PEG-ADA ERT
Reason: clarification, to prevent prematurely re-starting PEG-ADA based on previous study data
Protocol pages affected: 62
7. Add TCR V β panel assay to schedule of procedures
Reason: correction
Protocol pages affected: 110
8. Remove vector marking test from Day +1 (Schedule of Procedures)
Reason: not needed
Protocol pages affected: 110

9. Change description of allocating the back-up bone marrow
Reason: clarification based on technical procedures at UCLA
Protocol pages affected: 14, 56, 58, 64, 113, 114
10. Correct time-points for blood collection of samples for busulfan pharmacokinetics
Reason: consistency
Protocol pages affected: 71, 115
11. Add a scientific reference
Reason: update
Protocol pages affected: 30, 103
12. Update Appendices C, E, and G
Reason: update
Protocol pages affected: 120, 126, 131

Changes made 13 May 2013 (ver. 1.4) from previous version dated 23 April 2013

1. Clarified the objectives
Reason: to emphasize that safety is the primary objective
Protocol pages affected: 11, 42, 47, 54, 62, 71, 80
2. Added IND #15440 to sample label
Reason: update
Protocol page affected: 59
3. Correct grammar (quantitation)
Reason: correction
Protocol page affected: 81

Changes made 03 July 2013 (ver. 1.4a) from previous version dated 13 May 2013

1. Added Hepatitis C as screening virology test
Reason: to be consistent with informed consent
Protocol pages affected: 52, 70, 111, 112
2. Change anti-epileptic drug prior to busulfan administration from dilantin/fenytoin to Keppra
Reason: hospital procedure
Protocol pages affected: 62, 72, 116

Changes made 01 October 2013 (ver. 2) from previous version dated 03 July 2013

1. Change Inclusion/Exclusion criteria to allow for different reference ranges established by different diagnostic labs and to align SCID definition with PIDTC guidelines
Reason: update
Protocol pages affected: 53, 114
2. Change the duration of busulfan administration from 2 to 3 hours
Reason: to be consistent with hospital practice
Protocol pages affected: 72, 118, [Appendix C](#)
3. Change the trade name drug “Keppra” to its generic name, levetiracetam
Reason: to allow clinical sites flexibility
Protocol pages affected: 73, 117
4. Specify the tests in chemistry and immune function panels and describe other tests
Reason: clarification
Protocol pages affected: 71, 112-114, 115, 120
5. Exclude DFSP as a malignancy that would halt enrollment because some ADA-deficient SCID patients will develop DFSP, and DFSP is not an exclusion criterion
Reason: clarification
Protocol page affected: 81, 87
6. Change the window for follow-up visits to be +/- 4 weeks to be consistent throughout the protocol
Reason: consistency
Protocol page affected: 119

Changes made 10 February 2014 (ver. 3) from previous version dated 01 October 2013

1. Allow for subjects to be transferred to the care of their home physician for monitoring 3 days after infusion of gene-modified cells
Reason: to allow for flexibility for out-of-town subjects and their families
Protocol pages affected: 65, 75, 119
2. Added additional investigators involved in patient care
Reason: add to protocol
Protocol pages affected: 17, 111
3. Correct error in time of busulfan administration (from 2h to 3h)
Reason: error
Protocol page affected: 123

Changes made 4 June 2014 (ver. 3.1) from previous version dated 10 February 2014

1. Change: Update “Table of Contents”
Reason: For accurate pagination
Protocol pages affected: iv-vii

[figure not shown]
2. Change: Reformat section titles and/or tables and/or margins
Reason: Change format for clarity, logical pagination and “Table of Contents” update function to work properly
Protocol pages affected: 10-12, 15-16, 18-19, 23, 107-108, 111-112, 114-115, 119-120, 123-125, 130-131, 135-136

3. Change: Updated investigators involved in patient care and updated organizational chart
Reason: Change in personnel and added new investigators to protocol
Protocol pages affected: 16, 17, 109, 113

4. Change: Add PBMC ADA Activity to the Schedule of Evaluations on page 114
Reason: Correction; test was omitted
Protocol pages affected: 113-114

Changes made 13 January 2015 (ver. 4.0) from previous version dated 4 June 2014

1. Increase number of subjects from 10 to 15
Reason: Enrollment of 10 subjects was fulfilled and more subjects have been identified. Preliminary data indicates that the protocol is safe and efficacious.
Protocol pages affected: 11, 45, 53, 88

3. Add prior allogeneic HSCT as an exclusion criteria
Reason: do not want to enroll subjects who have had previous exposure to chemotherapy
Protocol pages affected: 55

4. Update prophylactic medications requirements
Reason: to allow for reasonable clinical management of subjects
Protocol pages affected: 64-65, 67-68
5. Revise statistics due to increasing the number of subjects to 15
Reason: update
Protocol pages affected: 88
6. Add additional clinicians involved in subject follow-up
Reason: update
Protocol pages affected: 114
7. Clarify when T cell proliferative studies to PHA and tetanus should be conducted
Reason: clarification, test not necessary at every follow-up time point
Protocol pages affected: 115-116, 123
8. Clarify immunization schedule of treated subjects
Reason: to allow for reasonable clinical management of subjects
Protocol page affected: 124
9. Correct the volume of bone marrow that may be harvested. There was inconsistency in 2 places.
Reason: correct inconsistency
Protocol page affected: 74

Changes made 02 June 2015 (version 5.0) from previous version 4.0, 13 January 2015

1. Add that international normalized ratio (INR) may be used instead of prothrombin time (PT) for screening; INR is standard for coagulation studies
Reason: update
Protocol pages affected: 55, 72, 73, 116, 118
2. Increase screening window to 60 days and make consistent throughout protocol
Reason: window was too narrow and caused protocol deviations
Protocol pages affected: 54-55, 72
3. Increase the number of subjects to 20 and correct statistics
Reason: enrollment into the trial has occurred faster than anticipated. An additional 2 subjects (past 15) have been preliminarily identified

Protocol pages affected: 11, 45, 53, 85, 88

4. Correct the flask size for cell processing
Reason: error
Protocol page affected: 59
5. Change when TMP/SMX may be resumed after busulfan
Reason: clinically OK to start when neutrophils have recovered to 500
Protocol page affected: 68
6. Update clinicians involved in subject follow-up/care
Reason: update
Protocol pages affected: 114-115

Changes made 06 October 2015 (version 6) from previous version 5.0 02 June 2015

1. Update organizational chart
Reason: update
Protocol page affected: 18
2. Change the window for follow-up visits to be +/- 4 weeks to be consistent throughout the protocol
Reason: consistency
Protocol page affected: 51
3. Change method of ADA enzyme measurement in PBMC from the NIH, CLIA-quality TLC method to UCLA, research-quality Diazyme colorimetric method. Also add that erythrocyte ADA enzyme levels (from CLIA approved lab, Duke University) will also be recorded.

Protocol pages affected: 52-53, 64, 69-70, 87-88, 90-91.
4. Add that lymphocyte proliferation assay may be performed using ³H thymidine or CFSE
Reason: most labs are moving away from the radioactive assay to dye-based methods that can be measured on a flow cytometer
Protocol pages affected: 53, 70.

5. Add that confirmation of ADA enzyme deficiency can also include documentation of gene mutation known to cause disease
Reason: clarification
Protocol pages affected: 54, 73, [Appendix B](#).
6. Clarify the infection status eligibility for enrollment
From: “Evidence of active opportunistic infection or infection with HIV-1, hepatitis B, Hepatitis C, CMV, or parvovirus B 19 by DNA PCR within 60-90 days prior to bone marrow harvest.”
To: “Evidence of infection with HIV-1, hepatitis B, Hepatitis C, or parvovirus B 19 by DNA PCR within 90 days prior to bone marrow harvest. If other infection is present, it must be under control (e.g. stable or decreasing viral load) at the time of screening.”
Reason: clarification
Protocol pages affected: 55
7. Remove fungal stain requirement for final product release
Reason: fungal stain is not a requirement by the FDA for product release. It was added at the request of the UCLA IRB. However, including the stain delays the release of the final product (which is infused fresh) because the central lab at RRMC does not perform the test. The sample has to be driven to the Brentwood Annex for the stain. Additionally, the gram stain will also stain fungi, if present.
Protocol pages affected: 59-60, [Appendix B](#).
8. Add that for vector copy number (VCN) determination, digital droplet PCR (ddPCR) may be used
Reason: update of procedures
Protocol pages affected: 60, 65, 69-70, 83
9. Change the method of mycoplasma detection from the culture method to PCR
Reason: update to more rapid PCR method at Labs, Inc, which is a CLIA-accredited, FDA-registered, and TGA GMP-compliant laboratory
Protocol page affected: 60
10. Update PEG-ADA re-starting criteria to include change in measurement of ADA enzyme activity
Reason: to coordinate protocol procedures to be consistent with new changes
Protocol page affected: 64

11. Correct the tests included in a chemistry panel to be consistent throughout the protocol
Reason: correction/consistency
Protocol pages affected: 69, 73, [Appendix B](#)
12. Correct γ -retro to lentivirus
Reason: correct a mistake
Protocol page affected: 71
13. Remove requirement for recording height and weight at Day +1 after infusion, since it is already recorded at screening and baseline
Reason: not needed
Protocol page affected: 73, [Appendix B](#)
14. Correct blood draw times for determination of busulfan levels to be consistent with previous change
Reason: correct a mistake
Protocol page affected: 75
15. Coordinate descriptions of follow-up exams to be consistent with Schedule of Procedures ([Appendix B](#))
Reason: clarification
Protocol pages affected: 75-76, [Appendix B](#)
16. Update DSMB reporting requirements
Reason: update based on DSMB schedule
Protocol page affected: 84
17. Update data handling chart
Reason: update
Protocol page affected: 94
18. Update monitoring plan and responsibilities, delete duplicate paragraphs and sections noted
Reason: Update and correction. The trial enrolls a small number of subjects (up to 20) and thus monthly statistical analysis is excessive.
Protocol pages affected: 94-98.
19. Update list of clinicians involved in patient care

Reason: update

Protocol page affected: 17, 116

20. Update scientific references

Reason: update

Protocol pages affected: 26, 106.

Changes made 02 November 2015 (version 7) from previous version 6, 06 October 2015

1. Allow ANC ≥ 500 cells/mm³ alone to be acceptable inclusion criterion without the need for analysis of bone marrow biopsy/aspirate.

Reason: not necessary based on previous cases

Protocol page affected: 55

2. Clarify schedule for collecting myelosuppression labs; does not need to be for 6 weeks, if not clinically indicated.

Reason: consistency, clarification

Protocol pages affected: 51, [Appendix B](#)

3. Add monitor

Reason: update

Protocol page affected: 109

4. Update physicians involved in patient follow-up

Reason: update

Protocol page affected: 112

Changes made 30 March, 2016 (version 8) from previous version 02 November, 2015

1. Specify on the cell product label that the number of cells is total nucleated cells

Reason: clarification

Protocol page affected: 62

2. Add additional lab monitoring (weekly CBC/diff) of subjects who are slow to recover their cell counts until ANC is >500 cells/mm³

Reason: DSMB request

Protocol pages affected: 68, 117

3. Modify study stopping criteria

FROM:

If there is one death or two grade 4 toxicities (except grade IV busulfan-related hematologic serious adverse events {transient leukopenia, anemia, thrombocytopenia resolving within 42 days of transplant}, which are anticipated and will be reported, but will not be considered stopping criteria).

TO:

If there is one death or four grade 4 toxicities, (except grade IV busulfan-related hematologic serious adverse events {transient leukopenia, anemia, thrombocytopenia resolving within 42 days of transplant} which are anticipated and will be reported, but will not be considered stopping criteria). Additionally, neutropenia (a documented disorder of ADA-deficiency) occurring at any time, will be graded for severity but will not count towards the stopping rule.

Reason: change

Protocol pages affected: 83, 89-90

[REDACTED]

Changes made 21 October 2016 (version 9) from previous version 8, 30 March 2016
(pages referenced correspond to “tracked” protocol version)

1. Name investigational product “OTL-101” for easy reference
Reason: clarification
Pages affected: throughout document
2. Remove PBMC ADA activity from efficacy analysis
Reason: the PBMC ADA activity assay is research quality. We will use erythrocyte ADA activity, which is performed in CLIA lab at Duke, instead
Pages affected: 16, 124, 131, [Appendix B](#)
3. Update results of the γ -retroviral trial (MND-ADA)
Reason: update
Pages affected: 36-37

4. Update results and scientific references of insertional oncogenic events in other trials using retrovirus
Reason: update
Page affected: 39
5. Update other clinical trials using lentiviral vectors
Reason: update
Page affected: 41
6. Revised Trial Description and Study Objectives
Reason: revised to match updated statistical section
Pages affected: 52-57, 71
7. Update method of mycoplasma testing used for release of cell product
Reason: update
Page affected 63
8. Update DSMB
Reason: update
Page affected: 87
9. Update/revise statistics section ([Section 11](#))
Reason: revise and update
Pages affected: 87-100
10. Update data monitoring procedures
Reason: change from 80% to 100% source document verification
Page affected: 102
11. Update list of clinicians involved in patient care
Reason: update
Page affected: 123
12. Added Appendix for description of HSCT control arm. Reordered appendices to accept new addition
Reason: addition to align with new objectives/statistics sections
Pages affected: appendices H and I

Changes made 18 April 2017 (version 10) from previous version 9, 21 October 2016
(pages referenced correspond to “tracked” protocol version)

- [REDACTED]
- 2. Addition of level 4 sub-headers to sections 2 and 4.
Reason: administrative reasons allowing the headings to be part of table of contents.
Pages: Sections 2 and 4.
- 3. Primary objectives reworded and presented as separate bullets for ease of reading.
Reason: administrative change
Page: 12 (protocol summary) and 53
- 4. Secondary objectives, sub-headings of primary and secondary efficacy ave been removed and a list of secondary objectives are presented and aligned with the statistics section ([Section 11](#)). These revisions have also been aligned with the endpoints.
Reason: to align the text of objectives and endpoints with the statistical section
Pages: 12 (protocol summary), 53, 55 and 56.
- 5. Effects on ADA reconstitution on immune phenotype and function endpoint, text from introduction is bulleted as endpoint 11.
Secondary Efficacy End-point 11: Infection rates will be also measured under immune reconstitution as part of the efficacy assessment of a competent immune system.
Reason: administrative change.
Page: 57
- 6. Text added: Signed written informed consent according to guidelines of the IRB (UCLA [Office of Human Research Protection Program](#) and National Human Genome Research Institute (NHGRI) Institutional Review Board.
Reason: administrative change.
Page: 59.

7. Added correct level 2 sub-headings to [Section 7](#) in order for these headers to be captured in the table of contents.
Reason: administrative change.
Pages: 70 to 73.
8. Abbreviation correction for Electrocardiogram (EKG changed to ECG).
Reason: administrative change.
Page: 77.
9. Updated information for reporting safety events to the DSMB in [section 9.5.2.3](#) and 14.5, due to study oversight being transferred to the UCLA CTSI DSMB in September 2016.
Reason: to comply with UCLA CTSI DSMB standard procedures.
Page: 86 and 102.
10. The statistical considerations section of the protocol has been updated to be consistent with the statistical analysis plan generated for the study. This includes defining what data will be reviewed at the interim analysis at 6 months and the final analysis. The text is also refined to match the study objectives and endpoints, and distinguishes the different populations to be used for the safety and efficacy analyses.
Reason: Changes to [Section 11](#) (Statistical considerations) to be inline with the statistical analysis plan, the objectives, and endpoints of the study.
Pages: 89 to 95.
11. The auditor has changed from UCLA Office of Research Compliance to Clinical and Translational Science Institute, and all audit findings will be submitted to UCLA IRB, rather than both NIH and UCLA IRBs.
Reason: Administrative change.
Page: 99.
12. Added correct level 2 sub-headings to [Section 17](#) (Appendices) in order for these headers to be captured in the table of contents.
Reason: administrative change.
Pages: 114 to 146.

Changes made 13 November 2017 (version 11) from previous version 10, 18 April 2017
(pages referenced correspond to “tracked” protocol version)

1. Point viii was updated to note that obligations for the conduct of the study have been transferred by the IND holder to the CRO, TCTC.
Reason: Updated following involvement of the CRO, to be in line with standard practice.
Page: ii
2. The header for [Section 12](#) of the protocol was added to the Table of contents.
Reason: Administrative change.
Page: vi, 91.
3. A provision was added for collecting limited long-term data for withdrawn patients
Reason: tracking the survival of withdrawn patients, as well as their need for a rescue HSCT or reinstatement of PEG-ADA ERT, allows to collect better quality trial data.
Page: 75, 82, 83.
4. It was clarified that participants will be asked to continue scheduled evaluations if voluntary withdrawal occurs, post-treatment only.
Reason: Updated for clarity.
Page: 75 and 83.
5. The information to be collected in the CRF for all AEs was clarified, and a seriousness assessment was added to the list of fields to be completed for each AE. It was also noted that grade 3 and 4 AEs should be reported to the Sponsor, as well as to the PI or Study Coordinator, within 48 hours. Leukoproliferation was noted to be an “SAE of special interest” rather than an “expected SAE”, as it has never been observed in relation to OTL-101 so far.
Reason: Updated for clarity.
Page: 78 and 79.
6. Causality of Serious Adverse events will now be defined as definitely related, probably related, possibly related, unlikely related, or not related to the study agent. The text was also updated to more precisely define the nature of certain events, as Serious Adverse Reactions rather than SAEs.
Reason: Updated to be in line with standard practice.
Page: 80.

7. The language on the RAC reporting requirements was updated to be in line with current regulations. The word “expected” was removed as considered to refer only to adverse reactions or serious adverse reactions, and modified to “anticipated”.
Reason: Updated to be in line with currnt regulations and standard practice.
Page: 81.
8. The Statistical Considerations section ([Section 11](#)) was updated to include the Duke University HSCT control group, as well as to align the language in the section to the updated Statistical Analysis Plan. Use of the Duke University HSCT group as a comparator for the trial was agreed with the FDA at the End of Phase II meeting held on 29Sep2017.
Reason: The Duke HSCT control group was added to reflect FDA feedback, and the language modified to match the updated Statistical Analysis Plan.
Page: 84 to 88.
9. The text was updated to eliminate the requirement for completed eCRF pages to be printed and stored in the patients’ medical records, as this was burdensome for the site and the monitors.
Reason: Updated to reduce the burden on site and monitors.
Page: 93.
10. The name and email address of the Regulatory Coordinator were updated.
Reason: Administrative change.
Page:109.
11. Name and addresses were added for vendors involved in the study (GeneWERK, TechnoSTAT and Diamond Pharmacovigilance).
Reason: Administrative change.
Page: 112 and 113.
12. [Appendix H](#) was updated to include the Duke University HSCT control group, and to describe what data will be collected for this patient population. Use of this patient group as a comparator for the trial was agreed with the FDA at the End of Phase II meeting held on 29Sep2017. The paragraph regarding GOSH HSCT patients was updated to reflect the fact that 25 subjects treated between 2000 and 2016 were identified at GOSH, rather than 29. The Data Analysis section was also updated to clarify that severe infections will be considered in the comparison between trial data and HSCT data, rather than all infections.

Reason: the Duke HSCT control group was added to reflect FDA feedback; the number of GOSH HSCT patients identified was corrected; the data analysis section was updated for clarity.

Page: 139 to 141.

Changes made 28 March 2018 (version 12) from previous version 11, 13 November 2017
(pages referenced correspond to “tracked” protocol version)
